The Primary Mechanistic Outcome Measure for this study is percent change in MADRS scoreat one-month post treatment. **The Relevant Clinical Outcome Measure** is a reduction in depressive symptoms in treatment resistant outpatients diagnosed with MDD, as measured

by change in MADRS score. For secondary aims, the emphasis is on identifying the magnitude of effects (clinical significance, effect size) instead of statistical significance. Following the convention in imaging studies, we will conduct our primary analyses treating the contrast (baseline versus post) as one univariate outcome. We do not expect much variation across our narrowly defined subjects, although some variation is still possible. Given that, we will also analyze the data in the linear mixed effects modeling framework allowing for random intercepts (although this is not customary in imaging studies) as a way of sensitivity analysis.

Moderator/mediator investigation: We will explore various baseline variables as potential moderators of aiTBS. For this investigation, we will employ the MacArthur approach for moderator analysis. We will also examine potential mediators of rTMS effect using the MacArthur approach as well as contemporary causal mediation approaches, which we believe will provide valuable insights regarding the neuromodulation mechanism for the next phase of investigation.

Handling of missing data: As a way of assessing the impact of missing scan sessions, we will repeat our main analyses treating outcomes measured in the pre-aiTBS scan and in the 1-month post-aiTBS scan as multivariate outcomes. This will allow us to include all participants in the analysis as long as two of the three scans are available. In this analysis framework, missing data will be handled assuming that it is missing at random conditional on observed scan session data (maximum likelihood estimation). Analyzing the data using both univariate and multivariate analysis approaches will also serve as sensitivity analyses. Additionally, we will include the order of scan sessions in the model to account for the carryover and order effects.

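### The missing-data likelihood model names only the pre-treatment and 1-month scans, so as written it ignores the immediate-post value that its own two-of-three-scans rule counts

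*SAP*

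**What the plan says.** SAP section 9, Handling of missing data, opens: "As a way of assessing the impact of missing scan sessions, we will repeat our main analyses". It does this by "treating outcomes measured in the pre-aiTBS scan and in the 1-month post-aiTBS scan as multivariate outcomes". The next sentence reads: "This will allow us to include all participants in the analysis as long as two of the three scans are available". Estimation is by maximum likelihood, and "missing data will be handled assuming that it is missing at random conditional on observed scan session data". The paragraph then adds: "Analyzing the data using both univariate and multivariate analysis approaches will also serve as sensitivity analyses".

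The three scans are set out under Rationale for Study Design in the same section: before treatment, immediately after, and at 1 month. Protocol section 2a, Follow-up Time-Period, schedules clinical ratings and MRI at both post-treatment visits.

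Under Data Analyses the SAP says "we will conduct our primary analyses treating the contrast (baseline versus post) as one univariate outcome", and adds a sensitivity model "in the linear mixed effects modeling framework allowing for random intercepts" without listing its visits. It sets the primary measure as "percent change in MADRS scoreat one-month post treatment". Protocol section 2a, Outcome measures, sets the primary change at immediate post instead.

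**The concern.** A likelihood model with two outcomes needs only one of them to be observed, so a two-of-three rule is natural only for a three-visit model. The rule counts a scan that the model does not use.

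Maximum likelihood conditions only on what is in the likelihood. If the immediate-post value is outside it, the missing-at-random assumption cannot be conditional on that value. Yet early response is the most obvious observed predictor of who returns at 1 month.

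The trial has one arm, so the mean change is the whole efficacy result. If poor early responders leave, benefit at 1 month is overstated; if good ones leave, it is understated. The two-visit model is meant to reveal that, but it shares the weakness of the contrast it is compared with.

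**Working it through.** **1. The plan's own figures.** Sample size: ((1.960 + 0.842)/0.6)² = 21.8, so 22 by the normal approximation. The exact paired t needs 24 (power 80.4%); 23 gives 78.5%. The stated 23 is reproduced within one patient. With 20% missing, 30 × 0.8 = 24 remain. The point below uses only the 20%.

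**2. What each scan pattern contributes to a (pre, 1-month) model.**

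| Scans available | Values used | Immediate-post value |
|---|---|---|
| all three | pre, 1-month | unused |
| pre + 1-month | pre, 1-month | not available |
| pre + immediate | pre only | unused |
| immediate + 1-month | 1-month only | unused |

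**3. Bias when a missing 1-month value depends on the immediate-post value.** Assumed, not in the documents:
- MADRS SDs s1 = 5 at baseline and s2 = s3 = 11 at the post visits
- correlations r12 = r13 = 0.3, and r23 = 0.5 to 0.8
- logit P(missing) = a + b·z, where z is the standardised immediate-post score, |b| = 0.7 to 1.5, and a is set to give 20% missing

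Let δ be the mean of z among those seen at 1 month: δ = −E[z·P(missing)]/0.8. Numerical integration gives δ = −0.130 at b = 0.7 and −0.227 at b = 1.5. The sign reverses with b.

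- Complete pairs: bias = (s3·r23 − s1·r12)·δ
- Two-visit ML (1-month regressed on baseline, read at the full baseline mean): bias ≈ s3·(r23 − r12·r13)·δ
- Three-visit ML (regressed on baseline and immediate post): bias = 0

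Numbers in:
- b = 0.7, r23 = 0.5: complete pairs (5.5 − 1.5) × −0.130 = −0.52; two-visit 11 × 0.41 × −0.130 = −0.59.
- b = 1.5, r23 = 0.8: complete pairs (8.8 − 1.5) × −0.227 = −1.66; two-visit 11 × 0.71 × −0.227 = −1.77.

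Simulation (400,000 participants per setting) agrees:

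| b, r23 | Complete pairs | Two-visit ML | Three-visit ML |
|---|---|---|---|
| 0.7, 0.5 | −0.53 | −0.60 | −0.01 |
| 1.5, 0.8 | −1.63 | −1.77 | 0.02 |
| −1.5, 0.8 | +1.67 | +1.81 | 0.01 |

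At b = 0 all are zero. At 10% missing the two-visit bias is 0.3 to 1.0 points. In units of the 1-month SD, the 20% range is 0.41 × 0.130 = 0.05 to 0.71 × 0.227 = 0.16. This depends only on the correlations, so it serves for connectivity too.

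**4. What the planned comparison would show.** With these MADRS SDs, the two analyses differ by 0.60 − 0.53 = 0.07 to 1.77 − 1.63 = 0.14 points, while each is off by 0.5 to 1.8. If all visits have equal SDs, as connectivity might, the complete-pair bias is (r23 − r12)·δ: 0.2 × 0.130 = 0.03 to 0.5 × 0.227 = 0.11 SD. The two-visit bias is then the larger one, 0.05 to 0.16 SD in the same direction. So the near-equality depends on the SDs. In neither case does the two-visit model correct the contrast.

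**5. Scale.** At n = 30 and 20% missing, the three-visit MADRS estimate has a simulated SD of 2.04 to 2.24 points, so the largest two-visit bias is 1.81/2.04 = 0.89 of a standard error. Precision is a minor matter: adding the third visit gives 0.88 to 1.00 times the two-visit variance.

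**The case against.** The strongest reply is that this is a slip of wording. The two-of-three rule and the three planned sessions point to a three-visit model, and the phrase about observed scan data may have been meant to cover the immediate-post scan. That is probably right about intent. It does not settle the matter, because the text supplies no model term for that scan, and an analyst following it would fit two visits.

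A reader might infer that the two sentences contradict each other, or that participants admitted by the rule cannot be analysed. The documents do not support that. Anyone with two of three scans has at least one of pre and 1-month, so can formally enter a two-outcome likelihood.

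A reader might also infer that the SAP's sensitivity analyses are uninformative as a set. That goes too far. The random-intercept model may use all three visits. If it does, its simulated bias is −1.11 against −1.63 for complete pairs (b = 1.5, r23 = 0.8) and −0.32 against −0.53 (b = 0.7, r23 = 0.5). That is partial protection, and it would show a shift of 0.2 to 0.5 points.

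Three further limits stand. The paragraph is written for scan sessions, and it reaches MADRS only if the undefined main analyses include it. Otherwise the affected outcome is connectivity, which the SAP treats as exploratory. Every input except the 20% is assumed, and that 20% includes unusable imaging, so it is on the high side for MADRS ratings. If the protocol's immediate-post endpoint governs, 1-month dropout does not bias it.

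**Conclusion.** The point holds as a defect in a stated sensitivity analysis. As written, the likelihood model omits a scheduled visit that its inclusion rule counts, and it cannot condition missingness on early response. If 1-month missingness depends on immediate response, agreement with the complete-pair contrast is weak reassurance.

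The size is modest: at 20% missing, about 0.05 to 0.16 SD of the 1-month outcome, or about 0.6 to 1.8 MADRS points. The MADRS figure applies only if the main analyses include MADRS and the endpoint is at 1 month. The bias takes the sign of who leaves and vanishes if dropout is unrelated to immediate response.

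A reader might infer that the primary MADRS result is biased or invalid. The documents do not show that. They give no dropout mechanism, SDs or correlations, they do not say clearly that this paragraph governs MADRS, and they disagree on the primary time point. The change is worth making because it is cheap, not because the error is large.

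**What to change.** In SAP section 9, Handling of missing data, name baseline, immediate post and 1 month as the outcomes of the likelihood model. Specify visit as a factor, an unstructured covariance, and a small-sample degrees-of-freedom correction such as Kenward-Roger. State that the model applies to connectivity and to MADRS, and that inclusion in the MADRS model does not depend on usable scans. Eligibility (protocol section 6h) already requires a baseline MADRS rating, so every participant has one. List the visits in the random-intercept model as well.

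Keep the paired t-test as the powered analysis and present the three-visit model as the missing-data analysis. Reconcile the primary time point between protocol section 2a and the SAP, and read the contrast there.

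Cost: a few sentences and one standard model, with no new data. Two drawbacks should be stated. The model estimates six covariance parameters (three variances, three covariances) from about 30 participants. It also does not fully protect if missingness follows the 1-month value itself: at 20% missing, under the assumed MADRS inputs, three-visit ML is then still off by 0.5 to 1.9 points, against 1.3 to 2.3 for two-visit ML.

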The subjects will undergo an MRI scan of the brain that will require about 1 hour in the MRI scanner. A structural MRI scan and an fMRI scan will be done using a 3T system at Stanford facilities.

During the scan, subjects will lie on the table in the magnet for 1 hour while the images are acquired. Instructions may be given through an auditory system. Subjects will wear earplugs and may be fitted for a bite bar to help them to keep their head still during the scans; for studies that enroll older adults, a bite bar will not be used so as to accommodate participants with dentures. These procedures have been used previously in younger and older adults alike, and do not cause undue distress in subjects. Brain images will be made using conventional MRI imaging (including functional and diffusion tensor

imaging).

Patients will undergo a minimum of 3 scans up to a maximum of 6 scans, each 1 hour in length.

Acquisition and data extraction:

Clinical interview ratings will be made by trained study personnel. Individual item scores will be recorded and then summed according to symptom cluster and scale definitions.

Outcome measures:

The primary outcome measure for this study will be change in MADRS score. The MADRS is a clinical assessment tool used to rate a patient's level of depression and is the standard scale used for depression research studies.

Secondary measures will include functional connectivity change of the sgACC to the DMN. Primary outcome will be assessed as the change between baseline and immediate post-stimulation, with secondary measures to include the change between baseline and immediate post- stimulation and 1-month post-stimulation.

Other secondary measures include clinical interview assessments, to be performed according to the timeline above, include:

HAMD-17 (Hamilton Depression Rating Scale 17-Item)
C-SSRS (Columbia Suicide Severity Rating Scale)
HAMD-6 (Hamilton Depression Rating Scale 6-Item)
MADRS (Montgomery-Asberg Depression Rating Scale)

b. Procedure Risks

These methods are the least risky because the intervals of stimulation have been shown to be appropriate for theta burst stimulation in the motor system with no adverse outcomes.

We don't anticipate any risk from the procedures themselves, aside from those mentioned in section 7a i.

c. Use of Deception in the Study

NA

d. Use of Audio and Video Recordings

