Monitoring participants depressive symptoms will allow the identification of individuals at risk of suicide and therefore the risk of this occurring can be minimized. The patient's psychiatrist will be immediately notified if participants show signs of suicidal ideation or display depressive symptoms which are worse than baseline (by 5 points on the HAMD compared to the HAMD score the patient had before study enrollment. If any study personnel believe a participant is at risk, the PI [name] (a psychiatrist) will be notified immediately and an emergency consultation between him and the participant will be had. If the PI considers it necessary, the patient will be referred for emergency psychiatric treatment.

If any participant displays an increased YMRS score ($>/=2$ points) on 2 questions, stimulation will be stopped to prevent any possibility of inducing hypomania or mania. If any of the research team or clinical staff believe that the participant may be showing signs of hypomania/mania, the YMRS will be administered by trained personnel immediately, the researchers will not wait until the daily assessments are conducted.

d. Study Conclusion

The experiment will terminate when the final participant has completed their treatment and all data has been analyzed.

e. Data Safety Monitoring Plan (DSMC)

i. Data and/or events subject to review

Adverse events, protocol deviations, aggregate data will all be frequently reviewed by the monitoring board (PD).

ii. Person(s) responsible for Data and Safety Monitoring

The Protocol Director.

iii. Frequency of DSMB meetings

NA

iv. Specific triggers or stopping rules

If there is evidence of significant risk to the participants such as multiple seizure events or worsening of psychiatric state in a large majority of the participants.

v. DSMB Reporting

NA

vi. Will the Protocol Director be the only monitoring entity? (Y/N)

Yes.

vii. Will a board, committee, or safety monitor be responsible for study monitoring? (Y/N)

NA

f. Risks to Special Populations

NA.

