Rationale for Study Design: The design will allow to assess the feasibility of modulating the neural circuitry underlying depression with accelerated intermittent theta-burst stimulation (aiTBS) alongwith the measuring the effects of this neuromodulation strategy on the underlying neural circuitry. The same subjects are utilized for all three MRI scan sessions, that is, for the pre-aiTBS scan session, the immediate post-aiTBS scan session and for the 1-month post-aiTBS follow-up scansession (to address functional connectivity aims). The rationale for using the same subject threetimes is to enable analysis of functional connectivity differences in the left DLPFC and dACC in response to aiTBS across time.

Sample Size

The study will be powered for an estimated effect size of Cohen's $d=0.6$ for change in Montgomery-Åsberg Depression Rating Scale (MADRS) between baseline and one month post treatment using within subject t-test. Prior investigations of iTBS of the L-DLPFC for treatment resistant depression reported an effect size of $d=1.337$, leaving our estimate conservative. We will set the probability of rejecting a true null hypothesis (Type 1 error, alpha) at 0.05 (two-sided) with 80% power. That will require a final sample size of 23 participants. This study will aim to recruit 30 individuals assuming approximately 20% missing data due to unusable imaging data or dropouts.

Interim Analyses and Stopping Rules

Because of the anticipated low level of adverse events of aiTBS and MRI, interim analysis of data,protocol and adverse events will occur by study staff at least once a year. Serious adverse events will be reviewed on a monthly basis, unless a more urgent review is requested. Only under extreme circumstances or if it were determined that a high level of side effects was due to aiTBS and/or MRI, would the PI be charged with breaking the study mask. This study will be stopped prior to its completion if: [1] the intervention is associated with adverse effects that call into question the safety of the intervention; [2] difficulty in study recruitment or retention will significantly impact the ability to evaluate the study endpoints; [3] any new information becomes available during the trial that necessitates stopping the study; or [4] other situations occur that might warrant stopping the study.

Data Analyses

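### The SAP ties its loss allowance and its only missing-data rule to MRI scans, although the primary endpoint is a MADRS rating, so missing MADRS data have no clear rule

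*SAP*

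**What the plan says.** **Endpoint.** The SAP (section 9, Data Analyses) states: "The Primary Mechanistic Outcome Measure for this study is percent change in MADRS scoreat one-month post treatment". The protocol (section 2a, Outcome measures) also makes MADRS change primary but at another visit: "Primary outcome will be assessed as the change between baseline and immediate post-stimulation". MADRS is a clinician's rating: "Clinical interview ratings will be made by trained study personnel".

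**Sample size.** SAP section 9, Sample Size, powers the study on MADRS change at d = 0.6, "between baseline and one month post treatment using within subject t-test", with two-sided alpha 0.05 and 80% power. It arrives at 23 participants and recruits 30, "assuming approximately 20% missing data due to unusable imaging data or dropouts".

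**Analysis.** The primary analysis takes one baseline-versus-post contrast per participant. A random-intercept mixed model is added as a sensitivity analysis; neither its outcome nor its analysis set is named.

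**Missing data.** The only paragraph on this subject is introduced as a check on missing scan sessions. It repeats the main analyses with the pre-treatment and one-month scan outcomes taken jointly, and says: "This will allow us to include all participants in the analysis as long as two of the three scans are available". Data are assumed missing at random given the scan data; MADRS is not named among the conditioning variables.

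Neither document defines an analysis population, gives a rule for a missing MADRS, or says whether ratings are still sought from someone who stops iTBS or declines MRI.

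**The concern.** A failed scan can reduce a MADRS sample only if scan status has some bearing on who is analysed for MADRS. The Sample Size paragraph implies that it does, and the missing-data paragraph speaks of the main analyses without limiting them to imaging. On that reading, a participant rated at every visit could be set aside because of the scanner.

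On the other reading, in which the paragraph covers connectivity only, the primary endpoint has no missing-data rule. The first-line contrast needs both ratings, so anyone without the post-treatment MADRS drops out of it by default.

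The stake is greater because every participant receives iTBS. There is no control arm in which similar losses might partly cancel, so any loss related to poor response would go directly into the reported effect.

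**Working it through.** **1. The plan's own figure.** Inputs from SAP Sample Size: d = 0.6, two-sided alpha 0.05, power 80%, paired t-test.
- Normal approximation: ((1.960 + 0.842)/0.6)² = 21.80, so 22.
- With the small-sample term 1.960²/2 = 1.92: 21.80 + 1.92 = 23.72, so 24.
- Exact noncentral t: 24 gives power 0.804; 23 gives 0.785.
- Inflation for 20% loss: 23/0.8 = 28.75, so 29; 24/0.8 = 30.

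The stated 23 and 30 are reproduced closely enough. The difficulty lies in who is counted as lost, not in the arithmetic.

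**2. The two readings side by side.**

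| | Rule covers MADRS | Rule covers imaging only |
|---|---|---|
| All MADRS ratings, too few usable scans | can be set aside | kept |
| No MADRS at the primary visit | handled given scan data, not given MADRS | out of the paired contrast; perhaps in the mixed model, if that model is for MADRS |
| Imaging failure in the MADRS loss figure | consistent | has no reason to be there |

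Neither column gives a satisfactory rule for the primary endpoint.

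**3. The rule against its own model.** The joint model uses only the pre-treatment and one-month scans, while the rule counts any two of three.

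| Scans available | Meets the rule | Supplies to the model |
|---|---|---|
| Pre + one month | yes | both values |
| Pre + immediate post | yes | pre only |
| Immediate post + one month | yes | one month only |

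A participant in the second row counts as included but gives no one-month value.

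**4. Possible size of the effect on the estimate.** The outcomes of lost participants below are assumptions, not figures from the documents. The SAP's 20% of 30 is 6 lost, leaving 24. Let d = 0.6 hold in the 24, on a common SD.
- Those lost had no change: (24 × 0.6 + 6 × 0)/30 = 0.48; gap 0.60 − 0.48 = 0.12 SD.
- Those lost worsened by 0.5 SD: (24 × 0.6 − 6 × 0.5)/30 = 11.4/30 = 0.38; gap 0.22 SD.
- Only 3 of the 6 are related to outcome, and the other 3 are imaging failures with an average response: (27 × 0.6 + 0)/30 = 0.54 and (27 × 0.6 − 3 × 0.5)/30 = 0.49; gaps 0.06 and 0.11 SD.

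**5. Possible size of the effect on the test.** In a simulation with 30 participants, normally distributed change, no true change and about 20% missing, the log-odds of being missing rose by 0.5 or 1.0 per SD of poorer outcome. The mean observed change was 0.10 or 0.17 SD, and the two-sided 5% test rejected 7.3% or 13.5% of the time. These mechanisms are also assumed.

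**6. What recovered ratings are worth.** Exact-t power at d = 0.6 is 0.785 with 23, 0.804 with 24 and 0.888 with all 30. Losses due only to imaging need not cost the MADRS analysis any of this.

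**The case against.** The strongest reply is that the missing-data paragraph is about imaging. It names missing scan sessions, conditions on scan data and adjusts for scan order, and its two-of-three rule belongs to a repeat analysis meant to keep more people in, not to the first-line analysis. The mixed model could also use incomplete MADRS records under missing at random.

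Much of this stands. A reader might infer that the SAP removes participants with complete MADRS ratings but no usable scan. No sentence says so; the Sample Size wording only suggests it. But accepting the imaging-only reading leaves the primary endpoint without a missing-data rule, and the mixed model does not fill the gap while its outcome and analysis set are unstated.

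A reader might also infer that participants who do worst will be lost, so that the result is biased toward benefit. The documents do not support this. In protocol section 7c, a rise in YMRS stops stimulation, not follow-up, and it signals possible hypomania or mania rather than a high MADRS. Emergency referral ("If the PI considers it necessary, the patient will be referred for emergency psychiatric treatment") is not described as withdrawal. Protocol section 2a schedules clinical assessments alongside MRI without making one depend on the other, and section 6k pays a bonus for missing no follow-up. Unusable images need not be related to mood.

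Finally, someone who leaves after the immediate-post rating is missing for the SAP's one-month endpoint but complete for the protocol's. The extent of the problem therefore depends on a conflict that the documents leave open.

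**Conclusion.** The point holds as a gap in specification. On either reading the primary MADRS analysis lacks a sound rule for missing data: valid ratings may be set aside because of scan status, or incomplete pairs are dropped with no defined alternative. The scan rule also does not match the model to which it is attached.

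That loss will be related to outcome is a possibility, not a finding. If all 6 expected losses were related to outcome, the analysed participants would overstate the all-participant effect by 0.12 to 0.22 SD under the assumed outcomes of no change and worsening by 0.5 SD. The overstatement shrinks if some losses are imaging failures unrelated to mood. A reader might take 30 − 23 = 7 as the number lost and obtain a larger gap, but the SAP's stated 20% is 6 of 30.

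The SAP should be amended, because the choice can change who is analysed and hence the single-arm estimate.

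**What to change.** 1. Define the MADRS and HAMD analysis set as all participants who received at least one iTBS session, whatever their scan status. Apply the scan rule to connectivity outcomes only, and align it with the visits that its model uses.
2. Analyse MADRS with a likelihood-based repeated-measures model using the baseline, immediate-post and one-month ratings. Take the contrast at the primary visit once the protocol (immediate post) and SAP (one month) have been reconciled. State how percent change is derived from the model.
3. State that the scheduled MADRS and HAMD ratings are still sought from participants who stop iTBS or decline MRI.
4. Add one missing-not-at-random sensitivity analysis, for example no improvement from baseline for those without the primary-visit MADRS. This example does not represent worsening, and the SAP should say so.
5. In Sample Size, state the expected MADRS loss separately from the expected imaging loss.

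The cost is SAP wording and one extra analysis. MADRS and HAMD-17 are already scheduled at all three visits in protocol section 2a. The reported effect may be smaller.

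### The two analyses offered as missing-data sensitivity checks both assume missing at random or something stronger, so comparing them cannot test loss that depends on the unseen one-month result

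*SAP*

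**What the plan says.** All of this is in SAP section 9.

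- **Primary outcome and main analysis.** Under Data Analyses, the outcome is percent change in MADRS at one month, and the main analyses treat the baseline-to-post contrast as a single outcome per participant. A random-intercept mixed model is added as a sensitivity analysis.
- **Missing data.** To assess missing scan sessions, the main analyses are repeated with the pre-treatment and one-month scans as joint outcomes. Anyone with two of the three scans is included. Here "missing data will be handled assuming that it is missing at random conditional on observed scan session data (maximum likelihood estimation". The paragraph then says: "Analyzing the data using both univariate and multivariate analysis approaches will also serve as sensitivity analyses".
- **Expected loss.** Under Sample Size, the plan is to "recruit 30 individuals assuming approximately 20% missing data due to unusable imaging data or dropouts".

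No planned analysis departs from missing at random: there is no delta adjustment, tipping point or imputation of non-response. The paragraph speaks of scans, and no separate rule for a missing MADRS score appears anywhere. It is also unclear whether the immediate post-treatment scan enters the multivariate model. The sentence naming the outcomes leaves it out, but the two-of-three rule suggests that it may be used.

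**The concern.** A change score exists only for a participant with both measurements, so the univariate analysis is a completer analysis. The multivariate analysis replaces that restriction with missing at random given what was observed. Neither lets the chance of being lost depend on the one-month value itself, and the mixed model states no departure from missing at random either.

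The protocol describes one treated group of 30 (Study Procedures; Planned Enrollment). The result is a pre-post change, with no control arm in which similar loss could offset the bias. If participants who did not benefit are less likely to return at one month, the estimated change is too large. A comparison of the two analyses might then be reported as evidence of robustness that it cannot supply. The estimate, and any effect size carried into a later study, would be inflated.

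**Working it through.** **1. The plan's own figure.** The inputs are d = 0.6, two-sided alpha 0.05, 80% power and a paired t-test (SAP, Sample Size), for which the plan states: "That will require a final sample size of 23 participants".
- Normal formula: ((1.960 + 0.842)/0.6)² = 21.8, so 22.
- Exact noncentral t: 24, with power 78.5% at n = 23 and 80.4% at n = 24.
- Allowance for loss: 23/0.80 = 28.75, so 29 against 30 recruited; 30 × 0.80 = 24 observed and 6 missing.

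The stated 23 is close enough and is not at issue.

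**2. Completers when loss depends on the unseen one-month change.** Assumptions, not given in the documents: change c is normal with mean 0.60 and SD 1, and non-improvers (c < 0) are three times as likely to be lost.
- P(c < 0) = Φ(−0.6) = 0.274.
- For 20% overall loss: 0.274 × 3q + 0.726 × q = 0.20, so q = 0.129 and 3q = 0.387.
- Contribution of non-improvers to the mean: 0.6 × 0.2743 − φ(0.6) = 0.1646 − 0.3332 = −0.1687. Contribution of improvers: 0.60 + 0.1687 = 0.7687.
- Completers' mean: (0.6125 × (−0.1687) + 0.8708 × 0.7687)/0.80 = 0.5661/0.80 = 0.71.
- For 10% loss, q = 0.0646 and 3q = 0.1937: (0.8063 × (−0.1687) + 0.9354 × 0.7687)/0.90 = 0.5830/0.90 = 0.65.

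**3. ML, by simulation.** Two-visit ML regresses the one-month score on baseline. Three-visit ML adds the immediate post-treatment score. Predictions are averaged over everyone. Assumed correlations run from 0.3 to about 0.82 between baseline and each later visit, and from 0.5 to 0.85 between the two later visits.

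| Loss (true d 0.60) | Completers | Two-visit ML | Three-visit ML |
|---|---|---|---|
| 20%, driven by unseen one-month change | 0.71 | 0.67–0.70 | 0.65–0.67 |
| 10%, driven by unseen one-month change | 0.65 | 0.63–0.64 | 0.62–0.63 |
| 20%, driven by observed immediate change | 0.66–0.68 | not tabulated | 0.60 |

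In the first row, three-visit ML falls to about 0.63 when the later visits correlate 0.85 with each other but only 0.5 with baseline. The mixed model was not simulated separately.

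**4. What the comparison can show.** In the first row, completers exceed two-visit ML by 0.01–0.04 (0.71 less 0.67–0.70), although both are wrong. Completers exceed three-visit ML by 0.04–0.06 in the first row, where ML is biased, and by 0.06–0.08 in the third, where it is correct. In single simulated trials of 30 (correlations 0.5 and 0.7), the gap between completers and three-visit ML has an SD of about 0.07. Neither agreement nor disagreement identifies the mechanism.

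**5. False improvement when the true change is zero.** With the same three-to-one loss, completers show a significant improvement in about 7.1% of trials at 20% loss and 4.2% at 10%, against a nominal 2.5%.

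**6. What a tipping-point analysis would show.** Take 24 observed with d = 0.6 and 6 missing with mean m. Overall mean = 0.6 − 0.2 × (0.6 − m), SE = 1/√24 = 0.204, 23 df.
- m = 0.6: t = 0.60/0.204 = 2.94, p = 0.007.
- m = 0 (no change): t = 0.48/0.204 = 2.35, p = 0.028.
- m = −0.3 (worse): t = 0.42/0.204 = 2.06, p = 0.051.

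**The case against.** A reader might infer that both analyses fail, and will agree with each other, whenever non-improvers are lost more often. The documents do not support that. Loss related to improvement is not by itself missing not at random. If a poor response is already visible at the immediate visit and that visit is in the model, ML returns 0.60 while completers give 0.66–0.68. ML is then right and the two analyses differ, as a useful check should. The two-of-three-scans rule allows this reading. Near-agreement arises mainly when the model holds only the pre-treatment and one-month scans.

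Other objections also have force:
- The 20% combines dropout with unusable images. A failed image need not remove a MADRS score or depend on improvement, so treating all six as lost MADRS scores is an upper illustration.
- The paragraph is about scans, so applying it to MADRS is an extension.
- Follow-up is short, and the protocol pays a bonus for complete attendance (section 6k), which may limit loss.
- At d = 0.6, significance survives setting all six missing participants to no change. At the prior effect that the SAP cites, d = 1.337, they would have to worsen by about 3.2 SD: (2.069 × 0.204 − 0.8 × 1.337)/0.2 = −3.2.

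These points limit the size and certainty of the bias. They do not answer the central one. Even three-visit ML stays too high when loss depends on the unseen result, and participants lost before the immediate visit gain nothing from including it. If the paragraph does not cover MADRS, the primary outcome has no missing-data rule at all.

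**Conclusion.** The point holds in a limited form. The SAP presents as sensitivity analyses two methods that do not vary the assumption in doubt. If loss depends on the unseen one-month result, all planned analyses err towards improvement. In the illustration, completers are about 18% too high at 20% outcome-related loss (0.71/0.60) and about 8% too high at 10% (0.65/0.60), with smaller errors for ML.

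These sizes rest on an assumed three-to-one loss ratio, assumed correlations and normal scores, none of which the documents supply. They do not show that such loss will occur, or that the two analyses must agree. The time point follows the SAP. The protocol (Outcome measures) instead sets the primary outcome at the immediate post-stimulation assessment, and that difference decides which observed visit can inform a missing one.

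This is an omission worth repairing cheaply. It does not make the study uninterpretable.

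**What to change.** Amend the missing-data paragraph of SAP section 9 as follows.

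1. Keep the ML analysis, label it the missing-at-random analysis, and state that the immediate post-treatment visit is included.
2. Apply it to MADRS as well as to the scans, so that the primary outcome has a stated rule.
3. Replace the claim that the two approaches serve as sensitivity analyses with a delta-adjusted (tipping-point) analysis of one-month MADRS over all treated participants. Impute missing values under missing at random, shift them in fixed steps to no change from baseline and beyond, and report the shift at which significance is lost.
4. Report missing MADRS scores separately from unusable images.

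The cost is a short SAP edit and one extra analysis of data already being collected, with no change to treatment or visits. The stated result may look less favourable.
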